## SUMMARY

**Rationale:** Patients undergoing cardiac surgery are at risk of developing perioperative complications and major adverse cardiac events, mainly related to both their preoperative status and type of surgical procedure. Postoperative exercise based cardiac rehabilitation (CR) is an effective therapy to prolong survival and improve quality of life. However, little is known about the effect on post-operative complications, quality of life and return to work of a combined pre- and post-operative CR program encompassing physical therapy, dietary counseling, psychological support and life style management compared to a CR program, which is provided only after cardiac surgery.

**Objective:** to determine whether a pre- and postoperative (PRE+POST) CR program improves the short (up to three months) and long term outcomes (up to one year) of the cardiac surgery (i.e. reduction in postoperative surgical complications, readmissions to hospital and major adverse cardiac events in conjunction with improvements in the physical component of health related quality of life), when compared to postoperative CR only (POST).

**Study design:** A Prospective Randomized Open controlled trial, Blinded End-point. Patients are randomized between two standard care CR programs. One group will start a POST CR program after surgery. The other group will be randomized to a combined PRE+POST CR program.

**Study population:** Patients (age > 18 years) admitted for elective coronary bypass surgery, valve surgery and/or aortic surgery

**Main study parameters/endpoints:** The primary outcome is a composite weighted endpoint of postoperative surgical complications, re-admissions to hospital, major adverse cardiac events and health related quality of life (two domains: physical functioning and physical problem), at three months and one year after surgery. Endpoints are determined by an independent endpoint committee, blinded to the group allocation. Secondary, the study focuses on physical health (cardiorespiratory fitness, muscle strength and functional status), psychological health (feelings of anxiety and depression), work participation, economics, lifestyle risk factors (physical activity and smoking behavior), self-efficacy and illness representations.

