### 1.1 OBJECTIVES

The primary aim of this study is to determine the effectiveness of a pre- and post-operative (PRE+POST) cardiac rehabilitation program compared to a phase II cardiac rehabilitation program that is provided only post-operative (POST), three months and one year after elective cardiac surgery. The effectiveness is primary measured with a composite endpoint of two subdomains of health related quality of life (physical functioning and physical problem), surgical complications, readmissions to hospital and major adverse cardiac events). The preoperative phase of the PRE+POST CR program consists of a outpatient CR program and the postoperative phase of an in- and outpatient phase. The postoperative phase of the POST CR program consists of an outpatient phase.

Secondary, this study is designed to evaluate the effect of the CR programs on:

- Prolonged stay at the intensive care, the occurrence atrial fibrillation and re-thoracotomies (*Complications and events*)
- Cardiorespiratory fitness, muscle strength and functional status (*Physical health*)
- Feelings of anxiety, depression and quality of life (*Psychological health*)
- Work participation
- Economic evaluation: health care costs and work-related costs
- Physical activity and smoking consumption (*Lifestyle risk factors*)
- self-efficacy and illness representations (*Potential mediators*)

The hypotheses are that patients who follow the PRE+POST CR program will benefit in terms of improved preoperative status, self-efficacy and illness perceptions compared to POST patients who follow postoperative CR only. In addition, PRE+POST patients may adopt a healthier lifestyle compared to patients who follow a POST CR program. This may prevent postoperative surgical complications, readmissions to hospital and major adverse cardiac events in conjunction with improvements health related quality of life, physical and psychological health. Furthermore, we expect that the PRE+POST CR program will be cost-effective in terms of a reduced health care use and an earlier return to work after cardiac surgery.

[figure not shown]

Figure 1: Intervention components, potential mediators and outcomes of the Heart-ROCQ study.

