#### 3.4 Sample size calculation

The composite weighted score consists of a summary score for worsening in functional status and the number of postoperative surgical complications, readmissions to the hospital and major adverse cardiac events (Table 2). The primary endpoint is partly adapted from the A-HeFT study.

The mean weighted score is estimated on 1.0 with a standard deviation of 0.9. This estimation is based on historical data of the UMCG (postoperative surgical complications and mortality), the Fitness Study - an on-going pilot study in the UMCG among the same population - (functional status), two literature studies: Iribarne et al., 2014 (hospital readmissions) and Serruys et al., 2008 (stroke and percutaneous interventions) and Meetbaar Beter database (re-interventions and myocardial infarction). A decrease of 0.3 means on average a decrease of one complication/event or worsening in functional status in 30% (or 10-20% decrease in major cardiac events or death) of the patients, which is considered to be clinically relevant. A group of 286 patients (143 in the PRE+POST group

and 143 in the POST group) achieve 80% power to detect a difference in the weighted score of 0.3, when alpha is set on 0.05.

The number of eligible patients is estimated to be 170 per year. We expect that 100 patients (60%) per year will be enrolled in the study. Therefore the estimated inclusion period is 3.5 years (n=350). In the total sample size (n = 350) a withdrawal of ±20% is incorporated. Because the mean score is estimated on different sources, different interim analyses are performed (section 7.4). Based on the interim analyses, the sample size can be adapted to ensure power.

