## 7. METHODS

### 7.1 Study parameters/endpoints

#### 7.1.1 Main study parameter/endpoint

The primary outcome is a composite weighted score of functional status, postoperative surgical complications, re-admissions to hospital and major adverse cardiac events at three months after surgery and one year after surgery. Each event, complication or worsening in functional status are considered as a score of 1 to 3 points. These points are summed to calculate the total score. Table 2 gives an overview of the primary endpoint. Functional status will be assessed with two health domains of the Medical Outcome Study 36-item General Health Survey (RAND-36 version 2): physical functioning and physical health problems. These two scales and the other six scales are evaluated separately as secondary outcomes.

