## 9. STATISTICAL ANALYSIS

### 9.1 Primary study parameter(s)

The primary endpoint is a composite score of functional status, postoperative surgical complications, hospital readmission and MACE. The summary score is calculated for each patient according to Table 2. Missing data on quality of life will be filled with the worst-case score for that component in the analysis. The mean and standard deviation for the summary scores of each group are calculated and handled as a continue variable. Multivariate analyses, inclusive multilevel analyses, are performed to determine time\*group differences at three months and one year after surgery.

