#### *Potential mediators*

The summary score of the different dimensions of illness representations (IPQ-R) and self-efficacy (CSA) are calculated and handled as continuous variable.

Mean and standard deviation are calculated for continuous variables. Multivariate analyses (inclusive multilevel analyses) are performed to determine time\*group differences for the continuous variables. Non-parametric tests are used if distributions are non-normal. In addition, descriptive statistics will be presented in median and (IQ) range. In all statistical analyses, a two-sided  $p<0.05$  is considered statistically significant.

Missing data analysis will be performed, meaning that the amount and nature of missing data will be studied and depending on this, adequate strategies to handle missing data will be applied (e.g. multilevel analyses). Patients are treated according to the intention to treat principles.

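### The primary score is analysed at two unranked visits while the trial is sized for one undated difference, so alpha 0.05 and 80% power are not assured

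*Combined protocol and SAP*

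**What the plan says.** Four places put the primary score at two visits and rank neither:

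- Summary: "at three months and one year after surgery"
- 1.1 Objectives: "three months and one year after elective cardiac surgery"
- 7.1.1 Main study parameter: "major adverse cardiac events at three months after surgery and one year after surgery"
- 9.1 Primary study parameter: "Multivariate analyses, inclusive multilevel analyses, are performed to determine" time-by-group "differences at three months and one year after surgery"

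The significance level appears at the end of 9.2 and covers everything: "In all statistical analyses, a two-sided" p below 0.05 counts as significant.

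Section 3.4 has a single set of inputs: "The mean weighted score is estimated on 1.0 with a standard deviation of 0.9". With 143 patients per arm the trial is said to "achieve 80% power to detect a difference in the weighted score of 0.3, when alpha is set on 0.05". No visit is attached to the mean, the SD or the difference.

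Section 9.4 triggers an interim when 40% of included patients have completed T6 (one year) and stops the trial at P<0.001. It does not say which contrast that P value belongs to. Section 3.4 refers to interim analyses in the plural, whereas 9.4 describes one.

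**The concern.** The plan does not say which result makes the trial positive. A model with arm, visit and their interaction yields several candidates: the arm difference at three months, the difference at one year, the average of the two, a joint test of both, and the interaction. These have different error rates and different power. The sample size calculation matches only one kind of test, a single two-arm comparison at one visit.

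Section 7.2 states that medical staff and researchers are not blinded, and 9.4 provides a look at the effect by arm. If the contrast is still open at that look, it could be chosen with the results in view. It could not be fixed credibly afterwards.

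**Working it through.** **Inputs from the plan:** difference 0.3, SD 0.9, 143 per arm, alpha 0.05 (3.4); two-sided testing (9.2); visits at three months and one year (7.1.1, 9.1).

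**Assumptions:** unless stated otherwise, 0.3 and SD 0.9 apply at both visits. The correlation between the two scores, ρ, is 0.5 to 0.9; the documents give no value. The upper part of that range is more plausible if both scores carry the same in-hospital items (prolonged ventilation, delirium, lung infection, ICU readmission).

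**1. The plan's own figure.** The standard error is 0.9 × √(2/143) = 0.1064, and 0.3 / 0.1064 = 2.82. A two-sided t-test at 0.05 has 80.2% power with 143 per arm and 79.9% with 142. The stated size therefore reproduces exactly, as one comparison at one visit.

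**2. Success at either visit, each tested at 0.05.** Under no effect, type I error = P(|Z₁| > 1.96 or |Z₂| > 1.96), with (Z₁, Z₂) bivariate normal and correlation ρ.

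**3. Success required at both visits.** Power = P(Z₁ > 1.96 and Z₂ > 1.96), each Z with mean 2.82.

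**4. Visit average.** The SD of the average is 0.9 × √((1+ρ)/2), which is 0.779 at ρ = 0.5 and 0.877 at ρ = 0.9. Power is calculated for 0.3 at both visits, and for an illustrative 0.2 at three months with 0.3 at one year (average 0.25).

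**5. Joint two-degree-of-freedom test of both visits.** The noncentrality is 2 × 2.82² / (1+ρ).

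| ρ | Either visit: type I error | Both visits: power | Average, 0.3 and 0.3: power | Average, 0.2 and 0.3: power | Joint test: power |
|---|---|---|---|---|---|
| 0.5 | 9.1% | 69.4% | 90.0% | 77% | 83.8% |
| 0.7 | 8.3% | 71.9% | 86.1% | 72% | 78.7% |
| 0.8 | 7.8% | 73.5% | 84.2% | 69% | 76.2% |
| 0.9 | 7.0% | 75.5% | 82.2% | 67% | 73.8% |

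**6. Interaction as the deciding test.** The quantity tested is the one-year difference minus the three-month difference. A constant benefit gives 0.3 − 0.3 = 0, so the test rejects 5% of the time, which is its alpha. If the effect grew by 0.15 between visits, power would be about 29% at ρ = 0.5 and 88% at ρ = 0.9.

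**7. One named visit.** Power is 80.2% if 0.3 and SD 0.9 describe that visit. With SD 0.8, 1.0 or 1.1 (illustrative) it is 88.5%, 71.5% or 63.2%. With an effect of 0.2 and SD 0.9 it is about 47%.

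**8. Alpha split, 0.025 per visit.** Power per visit at 143 per arm is 71.4%. Restoring 80% at each visit takes 173 per arm (80.2%), or 346 evaluable patients. That is 346 / 0.80 = 432.5, so 433 enrolled at 20% loss, or 346 × 350/286 = 423 at the protocol's own ratio of enrolled to evaluable.

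**The case against.** **One model, one test.** A time-by-group term is ordinarily one interaction test, and 9.3 uses the word multivariate for MANOVA, which would suggest one joint test. Either reading holds alpha at 0.05, and this stands. It does not rescue the power claim: the interaction cannot see a constant benefit, and the joint test has 80% power only at the lower correlations. Section 9.1 chooses neither.

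**One year is evidently the primary visit.** Table 2 counts readmissions up to one year, and the interim waits for T6. Both point that way, and N stands under that reading if 0.3 and SD 0.9 are one-year figures. However, four sections give three months equal standing, and 3.4 does not date its inputs.

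**The inflation is modest and conditional.** This is fair. No section says that either visit suffices. With shared in-hospital items the correlation is probably high, so 7% to 8% is more realistic than 9%.

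**Equal effects at both visits are unlikely.** This is also fair. Readmissions, reinterventions, infarction and stroke are counted up to one year, so a three-month score would probably have a lower mean and perhaps a different SD and effect. The two-visit power figures are illustrations. The objection also shows why the missing date in 3.4 matters.

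**The interim can adapt the sample size.** Sections 3.4 and 9.4 allow this, but a change in N does not settle which contrast decides.

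**Conclusion.** The point holds as a gap in the success rule. The stated alpha and power apply under some rules that the text permits and fail under others. If either visit counts, type I error is about 9% to 7%, more likely 7% to 8%. If both are required, power is about 69% to 76%. If the interaction decides, alpha holds, but a constant 0.3 benefit is found only 5% of the time. The first two figures rest on the assumed correlation of 0.5 to 0.9, and the power figure also on 0.3 and SD 0.9 at both visits.

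A reader might infer three stronger conclusions that the documents do not support:

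- *The trial is too small.* It is not shown to be: 143 per arm is correct for one comparison with the stated inputs.
- *The trial runs at 9% type I error.* That needs an either-visit success rule, which is nowhere written, and the lowest correlation considered.
- *Naming a visit, or using the visit average, settles alpha and power by itself.* A named visit delivers 80% only if 0.3 and SD 0.9 describe it. The average does so only if the effect is about 0.3 at both visits; with 0.2 at three months it gives about 77% to 67%. Nor does naming a contrast, by itself, guarantee 5% if the sample is extended after the effect has been seen, as 9.4 allows.

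This must be fixed before the first comparison by arm, because it is the trial's criterion for success.

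**What to change.** Before any comparison by arm, including any interim, put the following in 7.1.1 and 9.1 and align the Summary and 1.1:

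> The primary contrast is the between-arm difference in mean total score at [one year], estimated from a multilevel model with arm, visit and arm-by-visit, and tested at two-sided 0.05. The difference at [three months] is tested at two-sided 0.05 only if the first is significant. The arm-by-visit interaction is not the deciding test. The three-month score counts only items and events up to that visit.

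The last sentence is needed because Table 2 counts readmissions to one year and deep wound infection to 120 days. One year is the natural first choice, given Table 2 and the T6 trigger, but the sponsor should confirm it; the reverse order controls alpha equally.

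In 3.4, state which visit the mean of 1.0, SD of 0.9 and difference of 0.3 describe, and restate the power if that is not the primary visit. In 9.4, apply the P<0.001 rule to the same contrast.

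**Cost.** Text edits only, and N does not change. The downside is that an effect seen only at the second-ranked visit cannot be claimed as a primary success.

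**Alternative.** If both visits stay primary at 0.025 each, restate the power as about 71% per visit at 143 per arm. Only a wish for 80% at each visit separately raises N, to 173 per arm, which means about 423 to 433 enrolled.

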### 9.2 Secondary study parameter(s)

#### *Complications and events*

The incidence of atrial fibrillation, re-thoracotomies, prolonged stay at the intensive care unit and parameters of the primary endpoint are determined. In addition, group differences are tested by chi-square tests. Group difference for re-admissions to hospital and hospitalization days are tested with the Mann-Whitney test, because these variables are usually positively skewed.

#### *Psychological health*

For the PHQ and GAD, the total scores are calculated as the sum score of the respectively nine and seven items (resp. range 0 to 27 and 0 to 21). Sum scores of the PHQ and GAD are handled as continuous variables. A PHQ-9 change score of 5 or greater reflects a clinically relevant change. For the GAD, a change of 0.5 standard deviation is considered clinically relevant, which is according to the distribution based theory of Cohen.

For quality of life the scores of the eight subscales (physical role, physical functioning, general health, bodily pain, vitality, social functioning, emotional role and mental health) are calculated. In addition the two composite scores (the physical composite summary score and the mental composite summary score) are calculated. These scores and the score of the eight subscales are handled as continuous variable. A clinical relevant difference is defined as a minimal change according to Wyrwich et al., (2004)

### *Lifestyle risk factors*

Data collected with the SWA and the iPAQ questionnaire (T1, T4 and T6) are handled as continues variables. Energy expenditure at different intensities and METs measures of the SWA are exported. For the iPAQ, MET-minutes per week are calculated within each domain (work, transport, domestic and garden, and leisure) for walking (W), moderate-intensity activities (M), vigorous-intensity activities (V). In addition, total scores for walking (W), moderate- intensity activities (M), vigorous-intensity activities (V) and an overall grand total score are calculated. In addition, patients are categorized in three groups (low, moderate and high) according to the iPAQ manual. The sitting question will be handled as an additional indicator variable of time spent in sedentary activity. The incidence of low, moderate and high physical activity and time spent in sedentary activity are measured at T1, T4 and T6. In addition, the prevalence of smokers will be assessed at T1, T4 and T6. For smokers the number of cigarettes are handled as a continue variable.

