##### *PRE+POST group*

Patients who are randomized to the PRE+POST group receive a CR program consisting of three phases. 1) A preoperative optimization phase (3x p/wk, 4-6 weeks, before surgery), 2) a postoperative in-patient phase (15 to 18 days in rehabilitation center, second weekend at home) and, 3) an outpatient patient clinical rehabilitation phase (2x p/wk, 4 weeks). During each phase, patients will visit a physical therapist (group sessions of inspiratory muscle training (IMT), strength training, aerobic cycling and breath, cough and relaxation sessions), a dietician and a psychologist to optimize general health and receive advice on lifestyle, anxiety and stress management. Two additional components are coaching to stop smoking and coaching to return to work. These additional components are available for patients who smoke and/or are still working.

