
Starting approximately 3-6 weeks after surgery: POST-out phase
 
 
- Two to six week outpatient patient clinical rehabilitation period (A phase II rehabilitation program, based on the Dutch guidelines)
 
 
Physical therapy
 
 
- One to three times a week supervised sport activity
 
- Patients are encouraged to plan one sport activity by themselves.
 
 
Group education
 
 
- two to four group educations about risk factors and retaining a healthy lifestyle.
 
 
On indication:
 
 
- Prolongation of program to max. 16 weeks (8 to 12 weeks on average)
 
- Psychological counseling
 
- Dietician
 
	
Starting approximately 5 weeks after surgery: POST-out phase
 
 
- Four week outpatient patient clinical rehabilitation period (three times a week)
 
 
Physical therapy
 
 
- Two times a week supervised sport activity***
 
- Patients are encouraged to plan one sport activity by themselves.
 
- Two group educations in which patients will make a plan for exercise in home situation and discuss the experiences of this plan.
 
 
Life style management module
 
 
- Two group sessions about retaining a healthy lifestyle after rehabilitation supervised by a psychologist and dietician. (starting at the end of clinical phase or begin outpatient patient clinical rehabilitation period)
 
- Individual dietetics or psychological sessions on indication
 
 
Smoking and labor consultation on indication

\*IMT training ends when the intensity of the last preoperative training is reached; \*\* Depending on patients exercise tolerance; \*\*\* the following sports are included: aerobic cycle ergometry, sports and games, resistance training/ cardio fitness and swimming; Not available in each hospital

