### *Lifestyle risk factors,*

Physical activity is assessed using the Sensewear GECKO mini-armband (SWA) and the long version (27 questions) of the International Physical Activity Questionnaire (iPAQ). The SWA is worn on the upper arm and collects a variety of physiologic data through multiple sensors (a three-axis accelerometer, heat flux sensor, near-body ambient temperature sensor, and galvanic skin response sensor) to give a profile of physical activity. The reliability and validity is investigated in different studies

The iPAQ assesses physical activity undertaken in the prior 7 days, across 4 subcategories: (1) job-related physical activity; (2) transportation-related physical activity; (3) housework, house maintenance, and caring for family and (4) recreation, sports. In addition it includes a category about sedentary activity. Per category, the patient is asked to report the frequency (days per week) and duration (time usually spent per day) of moderate-intensity physical activity, vigorous-intensity physical activity, walking activities, bicycling, and time spent sitting. The iPAQ questionnaire has a good test-retest reliability (Spearman's rho of 0.8). Criterion validity of the self-report iPAQ against a CSA accelerometer is moderate (Spearman's rho of 0.3), which is comparable to most other self-reported physical activity questionnaires. From the data MET-minutes/ week can be calculated by weighting each type of activity by its energy requirements. There are three levels of physical activity (low, moderate and high) to classify the groups. Smoking behavior and history will be assessed with five questions.

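### The cigarette count is analysed "for smokers" with no value for quitters, so on the natural reading a fall in consumption that comes from quitting is largely hidden

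*Combined protocol and SAP*

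**What the plan says.** Section 1.1 lists "Physical activity and smoking consumption" among the secondary objectives. Section 7.1.1 (Lifestyle risk factors) says "Smoking behavior and history will be assessed with five questions", and section 7.3 schedules the smoking questions at T1, T4 and T6.

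The analysis is in section 9.2, Lifestyle risk factors. It first says that "the prevalence of smokers will be assessed at T1, T4 and T6". The next sentence is "For smokers the number of cigarettes are handled as a continue variable". The plan does not say whether smokers here means patients who smoked at T1 or patients smoking at the visit in question, and it assigns no number to a patient who has stopped.

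The general rules at the end of section 9.2 then apply: "Mean and standard deviation are calculated for continuous variables", followed by multivariate and multilevel models for time-by-group differences, with non-parametric tests where distributions are not normal. The missing-data text there is general and does not mention quitters. The same place commits to intention to treat.

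On the programmes, section 4 says of PRE+POST: "Two additional components are coaching to stop smoking and coaching to return to work". Table 1 lists smoking consultation, on indication, in all three rehabilitation phases of the PRE+POST column. The POST column lists no smoking consultation; its nearest entry is "two to four group educations about risk factors and retaining a healthy lifestyle".

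**The concern.** Smoking status at T4 and T6 is measured after randomisation, and one programme contains a component intended to change it. Section 1.1 also hypothesises that PRE+POST patients may adopt a healthier lifestyle, so unequal quit rates are what the plan itself expects.

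If the count is taken only in patients still smoking at each visit, those in whom the programme worked best leave the analysis. The remaining smokers in the two arms are no longer randomised groups, which sits badly with the intention-to-treat commitment. A quitter's consumption is known to be 0, yet it would enter as an absent value. At stake is the answer to the consumption objective: a real reduction could be reported as little or no difference, or, with some of the permitted methods, as a difference in the wrong direction.

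**Working it through.** **The plan's own figures.** The plan gives no smoking figure: no smoker prevalence, mean consumption or quit rate. Its sample size (286, section 3.4) concerns the composite score and does not bear on this point. All smoking figures below are assumptions.

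**Step 1: which set is meant.** The sentence on the count directly follows one that counts smokers visit by visit, so current smokers at each visit is the natural reading. Nothing in sections 7.1.1, 7.3 or 9.2 fixes the set at T1 or scores quitters 0.

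**Step 2: a small example.** Assume 30 baseline smokers per arm, 15 at 8 a day and 15 at 20 a day, with no change in those who continue.
- Baseline mean in each arm: (15×8 + 15×20)/30 = 420/30 = 14.0.
- PRE+POST: 9 light and 3 heavy smokers quit. Those left smoke 6×8 + 12×20 = 288 a day.
- POST: 3 light and 1 heavy smoker quit. Those left smoke 12×8 + 14×20 = 376 a day.

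The same data give three answers:
- All T1 smokers, quitters at 0: 288/30 = 9.6 against 376/30 = 12.5, so PRE+POST is 2.9 lower.
- Raw follow-up mean in current smokers: 288/18 = 16.0 against 376/26 = 14.5, so PRE+POST is 1.5 higher.
- Time-by-group comparison: each continuing smoker changes by 0, so the within-patient change is 0 in both arms. A random-intercept model fitted to this example (200 simulated runs, within-patient SD of 1 assumed, T1 and one follow-up) gave an average time-by-group estimate of 0.02 a day. The model in effect treats a quitter as having smoked on.

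The planned model therefore hides the 2.9 benefit. The reversal appears only in the raw follow-up mean, or could appear in a cross-sectional test at one visit.

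**Step 3: a range.** Assume baseline consumption with mean 12 and SD 7 (gamma), no change in continuing smokers, and quit rates (POST/PRE+POST) of 20/40%, 30/50% and 20/50%. Where quitting depends on consumption, its log-odds shift by −0.5 to −1.5 per SD (lighter smokers quit more) or by +0.5 (heavier smokers quit more). Entries are PRE+POST minus POST, cigarettes a day, at follow-up.

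| Who quits | Current smokers only (raw mean) | All T1 smokers, quitters at 0 |
|---|---|---|
| Unrelated to consumption | 0.0 | −2.4 to −3.6 |
| Lighter smokers more often | +0.7 to +2.3 | −1.8 to −3.3 |
| Heavier smokers more often | −0.5 to −0.8 | −2.5 to −3.8 |

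The first row can be checked by hand. With quitters at 0 the mean is 12×(1 − quit rate): 12×0.8 = 9.6 against 12×0.6 = 7.2 gives −2.4, and 9.6 against 12×0.5 = 6.0 gives −3.6. Among continuing smokers both means stay at 12. In the last row the current-smokers mean recovers about a fifth to a quarter of the difference (0.5/2.5 = 0.20, 0.8/3.8 = 0.21, 0.6/2.6 = 0.23).

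**Step 4: how many patients.** If 10% to 30% of 143 per arm smoke at T1 (assumed), that is 143×0.10 = 14.3 to 143×0.30 = 42.9 patients per arm. Any analysis of this outcome will be imprecise.

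**The case against.** Three objections deserve weight.

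First, the plan never says that quitters are excluded. Smokers could mean patients who smoked at T1, and the intention-to-treat commitment could be read as supporting that. This stands in part: the restriction to current smokers is an inference from an undefined term, though the likelier one. On the other reading the set and the zero for quitters still have to be written down.

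Second, quitting is not lost. Smoker prevalence at T1, T4 and T6 is already an outcome, and a reader would see fewer PRE+POST smokers beside any count. This also stands. But section 9.2 names no between-group test for prevalence: its chi-square tests are for complications and events, and those in section 9.3 are for baseline and surgery parameters and for the registry comparison. Prevalence also does not answer a question about consumption.

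Third, a reader might infer that the plan, as written, will make PRE+POST look worse because its coaching works. The documents do not support that. Reversal needs lighter smokers to quit preferentially, and it needs raw visit means or a cross-sectional test such as the non-parametric fallback could be. Under the time-by-group model the worked example gives about zero, and if heavier smokers quit more the raw difference favours PRE+POST but is too small. The example's quit pattern was also chosen to show the mechanism and is not a forecast.

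**Conclusion.** The point holds in a limited form. The plan leaves both the analysis set and the value for quitters undefined. On the natural reading, the cigarette count compares groups selected on a status that the PRE+POST programme targets. The likely consequence under the planned model is that a reduction achieved through quitting is largely hidden. With raw visit means or rank tests at a single visit, the result could lean towards POST or understate the benefit, depending on who quits.

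Under the assumed figures the concealed difference is 1.8 to 3.8 cigarettes a day. That size depends on the assumed baseline consumption, on quit rates 20 to 30 percentage points apart, and on continuing smokers not changing; none of these comes from the documents. The expectation that quit rates differ rests on smoking consultation being listed only for PRE+POST. The documents do not say that POST hospitals never offer it.

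One secondary lifestyle outcome is affected. The primary composite, the sample size and the stopping rule are not. The change is worth making before the data are analysed.

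**What to change.** Replace the sentence on the count in section 9.2 with a rule along these lines:
- Analyse cigarettes per day by randomised arm in all patients who smoked at T1. Section 7.2 places allocation after the baseline measurements, so this set cannot be affected by the programme.
- Score a patient known to have quit as 0 at T4 or T6. Keep this apart from unknown smoking status, which remains missing and falls under the missing-data strategy.
- Use a method suited to excess zeros and name it.
- Test the quit proportion between arms in the same set, naming the test.
- Label any summary restricted to current smokers as descriptive.

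The cost is a few sentences in the analysis section and slightly more analysis work, since the outcome will be zero-heavy. Smoking behaviour is already collected at T1, T4 and T6, so no new visits or questionnaires are needed.
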